6.2 PREPARATION/HANDLING/STORAGE/ACCOUNTABILITY

Study drug packaging will be overseen by the Roche clinical trial supplies department and bear a label with the identification required by local law, the protocol number, drug identification and dosage.

The packaging and labeling of the study medication will be in accordance with Roche standard and local regulations.

The investigational site will acknowledge receipt of IMPs and confirm the shipment condition and content. Any damaged shipments will be replaced.

Upon arrival of the IMPs at the site, site personnel will complete the following:

- Check the IMPs for damage.
- Verify proper identity, quantity, integrity of seals and temperature conditions.
- Report any deviations or product complaints to the Monitor upon discovery.

The qualified individual responsible for dispensing the study treatment will prepare the correct dose according to the defined dose-level utilizing the Pharmacy Manual.

The Investigator or delegate must confirm appropriate temperature conditions have been maintained during transit for all study treatment received and any discrepancies are reported and resolved before use of the study treatment.

Only participants enrolled in the study may receive study treatment and only authorized site staff may supply or administer study treatment. All study treatments must be stored in a secure, environmentally controlled, and monitored (manual or automated) area in

accordance with the labeled storage conditions with access limited to the Investigator and authorized site staff.

The Investigator is responsible for study treatment accountability, reconciliation, and record maintenance (i.e., receipt, reconciliation and final disposition records).

IMPs will either be disposed of at the study site according to the study site's institutional standard operating procedure (SOP) or returned to the Sponsor with the appropriate documentation. The site's method of IMP destruction must be agreed upon by the Sponsor. Local or institutional regulations may require immediate destruction of used IMP for safety reasons. The site must obtain written authorization from the Sponsor before any IMP is destroyed, and IMP destruction must be documented on the appropriate form.

Further guidance and information for the final disposition of unused study treatment are provided in the Pharmacy Manual.

6.3 MEASURES TO MINIMIZE BIAS: RANDOMIZATION AND BLINDING

6.3.1 Method of Treatment Assignment

Study NP40435 is a non-randomized open-label study. The specific treatment to be administered to the participant will be assigned using an IRT. An IRT User Guide will be provided to each site.

6.4 TREATMENT COMPLIANCE

The qualified individual responsible for dispensing the study treatment will prepare the correct dose according to the cohort assignment. This individual will write the date dispensed and participant number on the study treatment vial label and on the Drug Accountability Record. This individual will also record the study treatment number received by each participant during the study.

6.5 CONCOMITANT THERAPY

For the purpose of the study, RO7121661 is considered investigational medicinal product (IMP). All other medications given during the study are considered non-IMPs.

6.5.1 Permitted Therapy

Any medication or vaccine (including over-the-counter [OTC] or prescription medicines, approved dietary and herbal supplements, nutritional supplements) used by a participant during screening until the follow-up visit must be recorded along with reason for use, dates of administration (including start and end dates) and dosage information (including dose and frequency). The Medical Monitor *can advise* if there are any questions regarding concomitant or prior therapy.

All concomitant medications *or vaccines* should be reported to the Investigator and recorded on the Concomitant Medications electronic Case Report Form (eCRF). All therapy and/or medication administered to manage adverse events should be recorded on the Adverse Event eCRF.

Radiotherapy

Participants should not receive study treatment during radiation treatment.

The use of limited field palliative radiotherapy is allowed at any time during the study, **except for:**

- Days where RO7121661 is administered.
- During the DLT evaluation window.
 - If radiotherapy is administered during the DLT evaluation window, the participant will not be evaluable.

6.5.2 Prohibited Therapy

All medications (prescription and OTC) taken within 30 days of study screening will be recorded on the appropriate eCRF. As a general rule, no concomitant medication will be permitted, with the exception of medications to treat AEs and therapy for pre-existing conditions, unless the rationale for exception is discussed and clearly documented.

Use of the following therapies is prohibited during the study and for at least 28 days or 5 half-lives of the drug, whichever is shorter, prior to initiation of study treatment, unless otherwise specified below:

- Investigational or unlicensed/unapproved agents
- Immunotherapy/radio-immunotherapy
- Chemotherapy / targeted therapy
- Radiotherapy (with the exception of limited field palliative radiotherapy).
- Biologic agents (e.g., bevacizumab, cetuximab).
- Chronic use of steroids (inhaled and topical steroids are permitted) at baseline of >10 mg of prednisone/day or equivalent. Concurrent high doses of systemic corticosteroids will not be allowed.
- Administration of a live, attenuated vaccine within 28 days before Cycle 1 Day 1 or anticipation that such a live attenuated vaccine will be required during the study.

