9. Adequate renal function: serum creatinine ≤ 1.5 × ULN or creatinine clearance by Cockcroft-Gault formula ≥ 50 mL/min for participants in whom, in the Investigator's judgment, serum creatinine levels do not adequately reflect renal function. Cockcroft-Gault glomerular filtration rate estimation:

$(140-age)\times (weight in kilograms)\times (0.85 if female)$

72 × (serum creatinine in mg/dL)

- 10. Additional adequate laboratory parameters:
 - Serum albumin≥25 g/L (2.5 g/dL).
 - For participants not receiving therapeutic anticoagulation: Prothrombin time (PT) and activated partial thromboplastin time (aPTT)≤1.5×ULN or <2× ULN for participants with HCC.
 - For participants receiving therapeutic anticoagulation: stable anticoagulant regimen.
- 11. Negative HIV test at screening.
- 12. Negative hepatitis B surface antigen (HBsAg) test at screening.
- 13. Negative total hepatitis B core antibody (HBcAb) test at screening, or positive total HBcAb test followed by a negative hepatitis B virus (HBV) DNA test at screening.
 - The HBV DNA test will be performed only for participants who have a positive total HBcAb test.
- 14. Negative hepatitis C virus (HCV) antibody test at screening, or positive HCV antibody test followed by a negative HCV RNA test at screening.
 - The HCV RNA test will be performed only for participants who have a positive HCV antibody test.
- 15. Diagnosis of locally advanced and/or metastatic solid tumors with radiologically measurable disease according to RECIST v1.1.
 - Previously irradiated lesions should not be counted as target lesions unless clearly progressed after the radiotherapy.
 - Participants must have at least one measurable lesion (target lesion [TL]) not intended to be biopsied.
 - Lesions that are intended to be biopsied should not be counted as target lesions.

Contraception

16. Male and/or female participants

The contraception and abstinence requirements are intended to prevent exposure of an embryo to the study treatment. The reliability of sexual abstinence for male and/or female enrollment eligibility needs to be evaluated in relation to the duration of the clinical study and the preferred and usual lifestyle of the participant. Periodic

abstinence (e.g., calendar, ovulation, symptom-thermal, or post-ovulation methods) and withdrawal are not acceptable methods of contraception.

a) Female Participants

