For participants on treatment for at least 4 cycles, minor elective surgery will be permitted with resumption of treatment as soon as possible post-procedure, assuming normal recovery (see Section 7.1.1 for temporary interruption or dose delay). This can

be done to allow participants who could potentially benefit from RO7121661 to remain on the study treatment.

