9.5 INTERIM ANALYSES

It is anticipated that at least one interim analysis will be conducted in Part B of the study, with the earliest interim analysis taking place when at least participants have been enrolled per expansion, and participants have been followed for a minimum of 18 weeks. If no complete or partial responses are observed, enrollment will be stopped.

In general, predictive probabilities might be used to guide eventual additional interim analyses of clinical activity compared with expected activity from the SoC.

These futility analyses are not binding and may be overruled if other endpoints (such as DCR rate, DoR, PFS, or OS) show significant improvement over the expected benefit in the population.

Recruitment will not be interrupted while waiting for data maturity.

At any time during the study, parts, cohorts, and arms may be closed based on emerging data external to the study or operational reasons.

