1.1.3 Special Considerations regarding Lesion Measurability

Bone lesions, cystic lesions, and lesions previously treated with local therapy require particular comment.

Bone lesions:

Bone scan, PET scan or plain films are not considered adequate imaging techniques to measure bone lesions. However, these techniques can be used to confirm the presence or disappearance of bone lesions.

Lytic bone lesions or mixed lytic-blastic lesions, with identifiable soft tissue components, that can be evaluated by cross sectional imaging techniques such as CT or MRI can be considered as measurable lesions if the soft tissue component meets the definition of measurability described above.

Blastic bone lesions are non-measurable.

Cystic lesions:

Lesions that meet the criteria for radiographically defined simple cysts should not be considered as malignant lesions (neither measurable nor non-measurable) since they are, by definition, simple cysts.

'Cystic lesions' thought to represent cystic metastases can be considered as measurable lesions, if they meet the definition of measurability described above. However, if noncystic lesions are present in the same patient, these are preferred for selection as target lesions.

Lesions with prior local treatment:

Tumor lesions situated in a previously irradiated area, or in an area subjected to other loco-regional therapy, are usually not considered measurable unless there has been demonstrated progression in the lesion. Study protocols should detail the conditions under which such lesions would be considered measurable.

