2.3.2. Special notes on the assessment of target lesions

Lymph nodes: Lymph nodes identified as target lesions should always have the actual short axis measurement recorded (measured in the same anatomical plane as the baseline examination), even if the nodes regress to below 10 mm on study. This means that when lymph nodes are included as target lesions, the 'sum' of lesions may not be zero even if complete response criteria are met, since a normal lymph node is defined as having a short axis of < 10 mm.

Target lesions that become 'too small to measure': while on study, all lesions (nodal and non-nodal) recorded at baseline should have their actual measurements recorded at each subsequent evaluation, even when very small (e.g., 2 mm). However, sometimes lesions or lymph nodes which are recorded as target lesions at baseline become so faint on CT scan that the radiologist may not feel comfortable assigning an exact measure and may report them as being 'too small to measure'. When this occurs it is important that a value be recorded on the case report form:

If it is the opinion of the radiologist that the lesion has likely disappeared, the measurement should be recorded as 0 mm.

If the lesion is believed to be present and is faintly seen but too small to measure, a default value of 5 mm should be assigned and BML (below measurable limit) should be ticked (Note: It is less likely that this rule will be used for lymph nodes since they usually have a definable size when normal and are frequently surrounded by fat such as in the retroperitoneum; however, if a lymph node is believed to be present and is faintly seen but too small to measure, a default value of 5 mm should be assigned in this circumstance as well and BML should also be ticked).

To reiterate, however, if the radiologist is able to provide an actual measure, that should be recorded, even if it is below 5 mm and in that case BML should not be ticked (BML is equivalent to a less than sign <).

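### No rule says how response is scored after on-study palliative radiotherapy to a target lesion, so radiotherapy shrinkage can count as a confirmed response in the primary ORR

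*Combined protocol and SAP*

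**What the plan says.** **Permission.** Section 6.5.1 says "The use of limited field palliative radiotherapy is allowed at any time during the study", except on dosing days and in the DLT window. Section 6.5.2 repeats the exemption within its list of prohibited therapies: "Radiotherapy (with the exception of limited field palliative radiotherapy". Neither section distinguishes target from non-target sites.

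**Measurement on study.** Section 8.1.1 requires all measurable disease documented at screening to be re-assessed at every later tumour evaluation. Appendix 7, Section 2.3.2 adds that lesions "recorded at baseline should have their actual measurements recorded at each subsequent evaluation, even when very small". Under Appendix 7, Section 2.3.1, PR is a fall of 30% or more from baseline in the summed target diameters.

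**Lesions irradiated before entry.** Criterion 15 says "Previously irradiated lesions should not be counted as target lesions unless clearly progressed after the radiotherapy". Appendix 7, Section 1.1.3 says lesions in an irradiated or otherwise locally treated area "are usually not considered measurable unless there has been demonstrated progression in the lesion", and asks study protocols to detail the conditions. Both rules concern the choice of lesions at baseline.

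**Analysis.** Section 9.4.2 bases primary ORR and DCR on the investigator's RECIST 1.1 assessment, with confirmation at least 4 weeks later. It makes participants not evaluable only when assessments are missing or absent. Section 9.5 says of the interim look: "If no complete or partial responses are observed, enrollment will be stopped".

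**The concern.** The plan restricts lesions irradiated before entry as target lesions, but has no matching rule for a lesion irradiated after entry. A target lesion chosen at baseline and irradiated later stays in the sum by default. If it shrinks, the sum falls, and the fall is credited to RO7121661 even if the drug did nothing to the untreated disease.

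ORR and DCR are primary endpoints of the expansion part. The cohorts are open-label, have no control arm and are assessed by the investigator, so no comparison would offset the error. DoR and PFS, also primary, inherit it. A falsely scored responder enters the DoR analysis. For PFS the direction is less clear: a smaller sum can hide growth elsewhere at one scan, but it also lowers the nadir against which later growth is judged. The exploratory iRECIST analysis has the same gap, because Appendix 8 fixes each lesion's category once assigned and the sponsor computes response by program from the recorded lesion data.

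**Working it through.** There is no planned figure to reproduce. Section 9.1 states no hypotheses, Section 9.2 gives no power or type I error basis, and the Part B cohort size is blanked in the public text. The check therefore follows the text and then illustrates the arithmetic.

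**1. Can radiotherapy come before a response scan?** The DLT window is 21 days (Section 4.1.2). The first on-study scan is at week 8, and scans follow every 8 weeks in year one (Table 1, footnote 6). A target lesion could be irradiated after day 21 and before the first scan, or between later scans. Palliative radiotherapy is not listed in that footnote as a reason to end tumour assessment.

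**2. Does any rule remove the lesion or void the time point?**
- Section 9.4.2: not evaluable only for missing or absent assessments.
- Appendix 7, Section 1.2.2: not evaluable when no suitable substitute imaging method exists.
- Appendix 7, Section 2.4.2: not evaluable when lesions are not imaged or cannot be read.
- Section 9.4.2, PFS censoring (also used for DoR): at the last tumour assessment if there is no progression or death.

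None is triggered by local treatment.

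**3. How much must the treated lesion shrink?** If it makes up a share s of the baseline sum and all other target lesions are unchanged, PR requires shrinkage of at least 0.30 / s in that lesion.

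- s = 1 (sole target lesion): 30%
- s = 0.625: 0.30 / 0.625 = 48%
- s = 0.5: 60%
- s = 0.4: 75%
- s = 0.3: 100%

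Below s = 0.3 the treated lesion cannot produce a PR alone. Criterion 17 foresees Part B participants with a single target lesion.

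**4. Worked example (assumed diameters).** Target lesions of 40 and 30 mm give a sum of 70 mm. The first is irradiated and shrinks to 18 mm; the second is unchanged. The new sum is 18 + 30 = 48 mm, and 48 / 70 = 0.686, a change of -31.4%. That is a PR. If the lesion stays small at the next scan and nothing else progresses, the PR is confirmed.

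**5. Effect on a cohort (assumed 20 to 40 participants).** One such case adds 1/40 = 2.5 to 1/20 = 5 percentage points. With exact 90% intervals (Section 9.4.2 specifies 90% but not the method):

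- n = 40: 0/40 gives 0 to 7.2%; 1/40 gives 0.1 to 11.3%.
- n = 20: 0/20 gives 0 to 13.9%; 1/20 gives 0.3 to 21.6%.

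If it were the only response at the interim look, the zero-response condition in Section 9.5 would not be met.

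**The case against.** **The documents are silent; they do not instruct anyone to keep a treated lesion.** This is correct. The Appendix 7 sentence quoted on re-measurement comes from a note about lesions too small to measure. But Section 8.1.1 independently requires all measurable disease to be re-assessed, so retention is the default. A careful investigator might mark the time point not evaluable, but without a rule this would vary by site.

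**Other rules narrow the route.** A lesion needing palliation may reflect progression, and Section 8.1.1 has symptomatic progression recorded as such. New lesions, or unequivocal progression of non-target disease, make the time point PD. Confirmation requires untreated disease not to progress across two scans. These points stand, but they do not close the gap: shrinkage from radiotherapy would normally persist to a confirmatory scan.

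**The example is built to pass.** It needs 22/40 = 55% shrinkage of the larger lesion, and with up to five target lesions many patients could not reach PR this way. This stands, and it limits frequency rather than possibility.

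**The analysis is descriptive only.** True, but ORR is still a primary endpoint and feeds the interim decision.

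Two stronger readings are tempting and unsupported:
- A reader might infer that an excised target lesion would be entered as 0 mm, because Section 6.6 says "For participants on treatment for at least 4 cycles, minor elective surgery will be permitted". That section does not describe tumour-directed surgery. The 0 mm entry in Appendix 7 rests on a radiologist's opinion that a faint lesion has disappeared.
- A reader might infer that one false PR forces a cohort to continue. Section 9.5 calls the futility analyses non-binding, allows for further interim looks guided by predictive probabilities, and lets cohorts be closed for external or operational reasons.

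**Conclusion.** The point holds for radiotherapy to target lesions. The permission is not limited to non-target sites, the measurement rules retain the lesion by default, and no not-evaluable or censoring rule responds to local treatment. Radiotherapy shrinkage can therefore enter the primary ORR as a confirmed response.

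Its size is unknown. The documents do not say how often target lesions would be irradiated or how much they would shrink, and cohort sizes are blanked. The 2.5 to 5 percentage points per case rests on an assumed 20 to 40 participants, and the -31.4% on assumed diameters. The futility consequence is limited to this: one such response, if it were the only one, would leave a non-binding rule untriggered.

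The plan gives no reason for restricting lesions irradiated before entry, and it admits them after clear progression. The argument rests on the missing on-study rule, not on a stated principle. The change should be made: it is cheap and protects a primary endpoint.

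**What to change.** Add to Section 9.4.2 and Appendix 7:

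1. Record the site and date of any on-study local treatment of a tumour lesion (radiotherapy, or tumour-directed excision if it occurs).
2. From the date a target lesion is treated, later time points can be only PD, judged on untreated or new lesions, or NE. No CR or PR can be first scored or confirmed from them.
3. Responses confirmed, and SD already established, before that date stand.
4. Participants made NE by this rule stay in the ORR and DCR denominator as non-responders. This needs saying because Section 9.4.2 treats not evaluable and non-responder as separate classes without fixing the denominator.
5. State the matching DoR and PFS handling: whether follow-up continues to progression in untreated or new lesions or death, or is censored at the last assessment before local treatment.
6. Report a sensitivity ORR and PFS that ignores the local treatment.

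The cost is a few sentences and, if not already collected, eCRF fields for site and date. ORR and DCR may be slightly lower, and an occasional genuine but not yet confirmed response may be lost; the sensitivity analysis would show how much this matters. The clinical permission for palliative treatment is unchanged.

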6.6 DOSAGE MODIFICATION

Instructions for RO7121661 administration, change of infusion rate, and interruption of infusion are provided in Section 6.1 and Section 7.

Participants who experience toxicities fulfilling the definition of a DLT in the first cycle, or DLT-equivalent toxicities in subsequent cycles should be discontinued from study treatment. Nevertheless, the Investigators, after discussion with the Sponsor, will have the option to reduce the dose of RO7121661 to the previous tolerated dose level, if participant is deemed to be deriving clinical benefit.

A delay of RO7121661 administration for up to two cycles, will be acceptable to allow for resolution of toxicity to NCI CTCAE Grade ≤ 2 for hematological toxicities or Grade ≤ 1 for non-hematological toxicities (with the exception of a toxicity considered as non-RO7121661 related).

If the toxicity does not resolve to NCI CTCAE Grade ≤ 2 for hematological toxicities or ≤ 1 for non-hematological toxicities and the participant is unable to resume treatment with RO7121661 after this time (omission of two doses), no additional doses will be administered and the participant will be withdrawn from study treatment, unless the participant exhibits a clinical benefit and this is discussed by the Investigator and the Medical Monitor. It should be noted that infusions/cycles not occurring at the anticipated schedule, are considered as delayed, not missed.

Further dose-reductions may be implemented once safety and toxicity data from the dose-escalation have been evaluated.

For participants with documented liver metastasis and elevated liver function test (LFT) results at baseline, further elevations of LFT results may not require dose interruptions if there are no progressive changes in the ALT and/or AST (less than a doubling) and if there are no progressive elevations in total bilirubin or international normalized ratio (INR).

Investigators are encouraged to contact the Sponsor for further guidance if needed. After Cycle 1 is completed, dose modifications should be discussed with the Sponsor. In these instances, a confirmation with the Sponsor is requested and documentation in the eCRF is requested. Treatment delays of up to 3 days due to logistical considerations (e.g., center closure for holiday) are generally acceptable and do not need to be discussed with the Sponsor. In no instance are cycles shorter than 14 days of duration (i.e. Q2W) allowed in this study.

For participants on treatment for at least 4 cycles, minor elective surgery will be permitted with resumption of treatment as soon as possible post-procedure, assuming normal recovery (see Section 7.1.1 for temporary interruption or dose delay). This can

be done to allow participants who could potentially benefit from RO7121661 to remain on the study treatment.

